1.5.1. Results of toxicology studies

i) Comprehensive metabolic panel

Results are tabulated in Table-2, in parts I and II. For all electrolytes, enzymes and protein measurements, each rabbit sample prior to injecting the peptide served as its own control. Results are presented as % difference for each rabbit at each time point and then as % average of the difference. The % difference averaged out < 25% except for bilirubin, which averaged 100%. We believe this is within the normal fluctuation range of 0.1 mg/dL to 1.2 mg/dL.

Table-2, Part I: Comprehensive Metabolic Panel

	Comprehensive Metabolic Panel Results															
	Protein	% DIff.	Albumin	% DIff.	Calclum	% DIff.	Glucose	% DIff.	Creatinine	% DIff.	Total Bill	% Diff.	Alk Phos	% DIM.	AST (SGOT)	% DIff.
A1 (11/09)	4.20	0.0	3.40	0.0	13.3	0.0	139.0	0.0	1.4	0.0	0.2	0.0	49.0	0.0	21.0	0.0
A2 (11/09)	4.50	7.1	3.50	2.9	13.1	1.5	172.0	23.7	1.3	7.1	0.2	0.0	50.0	2.0	17.0	19.0
A3 (11/14)	4.60	9.5	3.50	2.9	13.7	3.0	132.0	5.0	1.2	14.3	0.2	0.0	43.0	12.2	17.0	19.0
A4 (11/19)	4.20	0.0	3.30	2.9	13.3	0.0	137.0	1.4	1.3	7.1	0.2	0.0	41.0	16.3	14.0	33.3
A5 (11/26)	4.80	14.3	3.60	5.9	14.3	7.5	91.0	34.5	1.3	7.1	0.3	50.0	42.0	14.3	26.0	23.8
% Diff Avg.		6.19		2.94		2.41		12.9		7.14		10		8.98		19.05
B1 (11/09)	4.40	0.0	3.40	0.0	13.7	0.0	146.0	0.0	1.1	0.0	0.1	0.0	72.0	0.0	21.0	0.0
B2 (11/09)	4.40	0.0	3.50	2.9	13.6	0.7	199.0	36.3	1.0	9.1	0.2	100.0	70.0	2.8	22.0	4.8
B3 (11/14)	4.40	0.0	3.50	2.9	13.2	3.6	142.0	2.7	0.9	18.2	0.1	0.0	67.0	6.9	21.0	0.0
B4 (11/19)	4.50	2.3	3.60	5.9	14	2.2	141.0	3.4	1.0	9.1	0.2	100.0	60.0	16.7	21.0	0.0
B5 (11/26)	4.60	4.5	3.60	5.9	14.1	2.9	149.0	2.1	0.9	18.2	0.2	100.0	54.0	25.0	17.0	19.0
% Diff Avg.		1.36		3.53		1.90		8.90		10.91		60		10.28		4.76
C1 (11/09)	4.50	0.0	3.60	0.0	13.6	0.0	164.0	0.0	1.2	0.0	0.1	0.0	46.0	0.0	12.0	0.0
C2 (11/09)	4.80	6.7	3.70	2.8	13.2	2.9	201.0	22.6	1.2	0.0	0.3	200.0	50.0	8.7	12.0	0.0
C3 (11/14)	4.90	8.9	3.80	5.6	13.7	0.7	158.0	3.7	1.1	8.3	0.2	100.0	44.0	4.3	16.0	33.3
C4 (11/19)	4.60	2.2	3.60	0.0	13.7	0.7	162.0	1.2	1.2	0.0	0.2	100.0	40.0	13.0	15.0	25.0
C5 (11/26)	4.8	6.7	3.8	5.6	14.1	3.7	158	3.7	1.2	0.0	0.2	100.0	41	10.9	16	33.3
% Diff Avg.		4.89		2.78		1.62		6.22		1.67		100		7.39		18.33

Table-2, Part II: Comprehensive Metabolic Panel

	Comprehensive Metabolic Panel Results Part II													
	ALT(SGPT)	% DIff.	Urea-N	% DIff.	Sodium	% DIM.	Potassium	% DIff.	Chloride	% DIff.	CO2	% Diff.	Anion Gap	% DIff.
A1 (11/09)	28	0.0	24.0	0.0	141.0	0.0	4.3	0.0	106.0	0.0	22.0	0.0	13	0.0
A2 (11/09)	26	7.1	26.0	8.3	140	0.7	4	7.0	111	4.7	19	13.6	10	23.1
A3 (11/14)	27	3.6	25.0	4.2	142	0.7	4.3	0.0	112	5.7	21	4.5	9	30.8
A4 (11/19)	21	25.0	17.0	29.2	140	0.7	4	7.0	108	1.9	25	13.6	7	46.2
A5 (11/26)	29	3.6	25.0	4.2	143	1.4	4.2	2.3	105	0.9	22	0.0	16	23.1
% Diff Avg.		7.86		9.17		0.71		3.26		2.64		6.36		24.6
B1 (11/09)	57	0.0	20.0	0.0	141	0.0	4.4	0.0	108	0.0	25	0.0	8	0.0
B2 (11/09)	56	1.8	22.0	10.0	141	0.0	3.9	11.4	111	2.8	19	24.0	11	37.5
B3 (11/14)	55	3.5	20.0	0.0	140	0.7	4	9.1	110	1.9	21	16.0	0	12.5
B4 (11/19)	52	8.8	21.0	5.0	141	0.0	4.3	2.3	110	1.9	21	16.0	10	25.0
B5 (11/26)	62	8.8	19.0	5.0	140	0.7	4.2	4.5	198	83.3	23	8.0	8	0.0
% Diff Avg.		4.56		4.00		0.28		5.45		17.96		12.8		15
C1 (11/09)	29	0.0	21.0	0.0	139	0.0	4.1	0.0	110	0.0	21	0.0	8	0.0
C2 (11/09)	30	3.4	22.0	4.8	139	0.0	3.9	4.9	111	0.9	17	19.0	11	37.5
C3 (11/14)	28	3.4	24.0	14.3	141	1.4	3.8	7.3	111	0.9	21	0.0	9	12.5
C4 (11/19)	27	6.9	21.0	0.0	140	0.7	3.7	9.8	108	1.8	24	14.3	8	0.0
C5 (11/26)	31	6.9	24	14.3	139	0.0	4.1	0.0	108	1.8	22	4.8	9	12.5
% Diff Avg.		4.14		6.67		0.43		4.39		1.09		7.62		12.5

Abbreviations

Total Bili = Total Bilirubin Alk Phos = Alkaline Phosphatase AST(SGOT) = Aspartate aminotransferase ALT(SPGT) = Alanaine aminotransferase Urea-N = Urea-Nitrogen

ii) Co mpl

ete blood count and differential

Complete blood and blood differential analysis was performed on each rabbit blood sample obtained prior to peptide injection (control) and then at 10 min, 5d, 10d, and 17d post injection. Data are summarized in Table-3, parts I and II. The data are presented as % difference with respect to the control sample for the hematological parameters in each blood sample obtained after administration of the diagnostic agent. In none of the data points (except last reading for WBC in animal A) was the difference greater than 6% (well below 10%). These data too are consistent with the lack of evidence that the agent had induced any pharmacologic effect.

Table-3, Part I: Comprehensive Blood Panel

	Comprehensive Blood Panel Results													
	WBC	% Diff	RBC	% Diff	HGB	% Diff	HCT	% Diff	MCV	% Diff	MCH	% Diff		
A1 (11/09)	5.30	0.0	5.46	0.0	12.1	0.0	36.9	0.0	68	0.0	22.2	0.0		
A2 (11/09)	5.60	5.7	5.73	4.9	12.8	5.8	38.8	5.1	68	0.0	22.3	0.5		
A3 (11/14)	6.64	25.3	5.31	2.7	11.9	1.7	37.2	0.8	70	3.1	22.4	0.9		
A4 (11/19)	4.80	9.4	5.10	6.6	11.4	5.8	36.3	1.6	71	4.4	22.4	0.9		
A5 (11/26)	7.40	39.6	5.91	8.2	13.4	10.7	41.7	13.0	71	4.4	22.7	2.3		
% Diff Avg.		16.00		4.51		4.79		4.12		2.38		0.90		
B1 (11/09)	6.90	0.00	5.81	0.00	12.6	0.00	38.4	0.00	66	0.00	21.7	0.00		
B2 (11/09)	6.50	5.80	5.78	0.52	12.4	1.59	38.3	0.26	66	0.00	21.5	0.92		
B3 (11/14)	6.20	10.14	5.07	12.74	10.9	13.49	34.4	10.42	68	3.03	21.5	0.92		
B4 (11/19)	6.10	11.59	5.51	5.16	12.1	3.97	38.0	1.04	69	4.55	22.0	1.38		
B5 (11/26)	6.90	0.00	5.72	1.55	12.6	0.00	39.9	3.91	70	6.06	22.0	1.38		
% Diff Avg.		5.51		3.99		3.81		3.13		2.73		0.92		
C1 (11/09)	5.50	0.00	6.02	0.00	12.5	0.00	38.5	0.00	64	0.00	20.8	0.00		
C2 (11/09)	5.10	7.27	6.34	5.32	13.2	5.60	40.6	5.45	64	0.00	20.8	0.00		
C3 (11/14)	5.60	1.82	5.90	1.99	12.3	1.60	38.4	0.26	65	1.56	20.8	0.00		
C4 (11/19)	4.90	10.91	5.65	6.15	11.8	5.60	37.3	3.12	66	3.13	20.9	0.48		
C5 (11/26)	4.9	10.91	6.14	1.99	12.8	2.40	40.6	5.45	66	3.13	20.8	0.00		
% Diff Avg.		6.18		3.09		3.04		2.86		1.56		0.10		

Table-3, Part II: Comprehensive Blood Panel

	Comprehensive Blood Panel Results Part II													
	MCHC % Diff RDW % Diff PLT % Diff MPV %													
A1 (11/09)	32.8	0.00	13.9	0.00	231	0.00	7.8	0.00						
A2 (11/09)	33.0	0.61	14.0	0.72	223	3.46	7.7	1.28						
A3 (11/14)	32.0	2.44	15.4	10.79	236	2.16	7.6	2.56						
A4 (11/19)	31.4	4.27	15.0	7.91	236	2.16	7.4	5.13						
A5 (11/26)	32.1	2.13	14.6	5.04	251	8.66	7.5	3.85						
% Diff Avg.		1.89		4.89		3.29		2.56						
B1 (11/09)	32.8	0.00	13.2	0.00	284	0.00	8.1	0.00						
B2 (11/09)	32.4	1.22	13.1	0.76	271	4.58	8.0	1.23						
B3 (11/14)	31.7	3.35	14.4	9.09	273	3.87	7.9	2.47						
B4 (11/19)	31.8	3.05	14.5	9.85	275	3.17	7.8	3.70						
B5 (11/26)	31.6	3.66	14.2	7.58	275	3.17	7.9	2.47						
% Diff Avg.		2.26		5.45		2.96		1.98						
C1 (11/09)	32.5	0.00	13.4	0.00	257	0.00	7.2	0.00						
C2 (11/09)	32.5	0.00	13.5	0.75	261	1.56	7.3	1.39						
C3 (11/14)	32.0	1.54	14.0	4.48	240	6.61	7.2	0.00						
C4 (11/19)	31.6	2.77	13.5	0.75	235	8.56	7.5	4.17						
C5 (11/26)	31.5	3.08	13.3	0.75	244	5.06	7.2	0.00						
% Diff Avg.		1.48		1.34		4.36		1.11						

ii) Body Weight

The animal body weights are summarized in Table-4. No animal suffered any body weight loss, suggesting that the peptide administration induced no adverse events leading to reduced dietary intake, altering animal body chemistry, or physiology that would adversely influence body weight. In fact, there was only an increase in the body weight, which is an expected normal phenomenon indicating normal health in all three animals.

Table-4: Rabbit Body Weights. Peptide injected: 28.5 ug/Kg. Total Peptide Injected: Rabbit A: 99.47 ug Rabbit B: 88.92 ug Rabbit C: 93.20 ug

Day	Date	Rabbit A	Rabbit B	Rabbit C
Day 0(injection day)				
Before injection	11-08-2007	3.49kg	3.12kg	3.27kg
10 min after injection	11-08-2007	Same	Same	Same
Day 5	11-13-2007	3.53kg	3.14kg	3.24kg
Day 10	11-19-2007	3.60kg	3.15kg	3.30kg
Day 17(sacrificed)	11-26-2007	3.66kg	3.27kg	3.43kg

iii) Cyclic Adenosine Monophosphate

21

The data on determination of serum cAMP (pmol/mL) in all three rabbits are given in Table-5. Data strongly show that in none of the rabbits, at any time during the 17 day experimental period, was there any statistically significant change (p = 0.34 or greater) in cAMP. The normal serum cAMP range in rabbits is 12.76-20.93 pmol/mL. The cAMP values in rabbits B and C were well within this range. In rabbit A however, the control serum cAMP value was 21.095. At the 10 min time point, this value was 21.78 and at day 10 it was 22.22. These values are not statistically, significantly different within themselves. These data too indicate that the cAMP levels were not altered by the administration of the peptide.

Table-5: Rabbit Serum cAMP Levels

cAMP Concentration (pmol/mL)										
Date Rabbit Rabbit Rabbit Average										
Day 0 (Injection Day) Before Injection	21.095	16.505	12.95	16.85±4.085						
Day 0 (Injection Day) 10 min After Injection	21.78	16.42	16.59	18.26±3.05 (p = 0.66)						
Day 5	19.36	16.67	15.03	17.02±2.19 (p = 0.915)						
Day 10	22.22	16.67	12.95	17.28±4.67 (p = 0.91)						
Day 17 (sacrifice)	12.26	16.07	13.82	14.05±1.92 (p = 0.34)						

iv) Histology

The animal histology data are presented in Table-6 (signed by [name], Professor of Pathology) and in Fig. 5 as stated by [name], no specific pathologic changes in organs examined were induced at any time in any of the animals.

Figure 5: Pathologic Representation of Tissue from a Normal and Treated Rabbits (400x)

[figure not shown]

Table-6: Pathologic Changes in Normal and Treated Rabbits

Н	efferson Iniversity ospital Health Sys Januan	, 7 2008						
Jefferson	Health Sysuaniual	7, 2006						
homas Jeffi niversity Ho homas Jeffe Iniversity Ho	Profess Room 2 Thomas [name] Philade		iology rson Alum n Universi et					
Division	noitel for							
efferson Hos leuroscience		perimenta	al Tissues					
ord Road Ca								
lethodist Hos lursing Cent	spital Dear Di er	r. [name]:						
	I have r no histo	eviewed to pathologi	he normal ic change	tissue cor between th	ntrols and t ne experim	he injected ental group	animals.	I found
	Light Micro	scopic Re	esults (Tab	ole 6)				
	Specimen	Heart	Lung	Liver	Spleen	Kidney		
	N	NSPC*	NSPC	NSPC	NSPC	NSPC		
	N A	NSPC*	NSPC	NSPC	NSPC	NSPC		
	•			Account them.				
	Α	NSPC	NSPC	NSPC	NSPC	NSPC		
	A B	NSPC NSPC	NSPC NSPC	NSPC NSPC	NSPC	NSPC NSPC		
	A B C * No Specification of the second of	NSPC NSPC NSPC It is a second of the seco	NSPC NSPC NSPC Ogic Change	NSPC NSPC NSPC	NSPC	NSPC NSPC		

v) Conclusion

These data in all three rabbits for 17 days after the administration of the highest (x100) peptide concentration dose did not show any pharmacologic effect in any parameter studied. We therefore concluded that the studies in lower concentration (x10 and x50) doses would be unnecessary, and we could not justify sacrificing so many otherwise normal rabbits.

1.6 Radiation Dosimetric Calculations

The mouse tissue distribution data obtained at 4hr and 24hr post injection was converted into % ID/organ and normalized for a kg body weight. All organs were weighed and average weight was used. Blood weight was estimated at 7% of the body weight, intestine at 40% body weight (32) and muscle at 9.3% body weight (33). Dosimetric calculations were performed using OLINDA/EXM 1.0 program obtained from Vanderbilt University. Data, the effective dose equivalent, is presented in Table-7 in mSv/mBq and rem/mCi.

Table-7: Estimated Absorbed Radiation Dose for Cu-64-Peptide

	Estimated Radiation Dose			
Target Organ	mSv/MBq	rem/mCi		
Adrenals	1.81E-02	6.71E-02		
Brain	3.10E-04	1.15E-03		
Breasts	4.83E-03	1.79E-02		
Gallbladder Wall	2.71E-02	1.00E-01		
LLI Wall	8.77E-03	3.25E-02		
Small intestine	2.09E-01	7.72E-01		
Stomach Wall	1.05E-02	3.87E-02		
ULI Wall	2.17E-02	8.01E-02		
Heart Wall	1.43E-01	5.30E-01		
Kidneys	2.73E-01	1.01E+00		
Liver	2.47E-01	9.14E-01		
Lungs	4.08E-02	1.51E-01		
Muscle	1.17E-02	4.32E-02		
Ovaries	1.27E-02	4.70E-02		
Pancreas	1.66E-02	6.14E-02		
Red Marrow	6.73E-03	2.49E-02		
Osteogenic Cells	4.63E-03	1.71E-02		
Skin	2.71E-03	1.00E-02		
Spleen	3.20E-03	3.45E-01		
Thymus	7.74E-03	2.86E-02		
Thyroid	1.81E-03	6.71E-03		
Urinary Bladder Wall	4.31E-03	1.59E-02		
Uterus	1.16E-02	4.28E-02		
Total Body	1.76E-02	6.53E-02		

For whole body imaging, (Group-A, please see section 1) we shall enroll 6 patients. In order to determine optimal image quality, we shall inject 2 patients with 3 mCi ($\pm 10\%$), 2 patients with 3.5 mCi ($\pm 10\%$) and 2 with 4 mCi ($\pm 10\%$). Image quality will be determined by a physician. Imaging time shall be approximately 45 mins.

Patients in group B will undergo PEM imaging using only the dose as determined from above. However, this dose shall not be more than 4±10% mCi. It is estimated that the dose received by kidneys, (total) blood, gall bladder wall, lungs, pancreas, uterus, and osteogenic cells will be high among all organs. However, the overall absorbed radiation dose is less than that from the commonly used diagnostic dose of 5-10 mCi of Ga-67 (Table-8) (34).

Table-8: Radiation Dosimetry for Ga-67

Estimated Radiation Dose (mGy/						
ORGAN	mGy/MBq	rad/mC				
Adrenals	1.3E-01	4.7E-01				
Brain	5.4E-02	2.0E-01				
Breasts	4.6E-02	1.7E-01				
Gallbladder Wall	8.3E-02	3.1E-01				
LLI Wall	2.6E-01	9.7E-01				
Small Intestine	8.6E-02	3.2E-01				
Stomach	6.9E-02	2.6E-01				
ULI Wall	1.5E-01	5.4E-01				
Heart Wall	6.7E-02	2.5E-01				
Kidneys	1.1E-01	4.2E-01				
Liver	1.1E-01	4.2E-01				
Lungs	6.1E-02	2.3E-01				
Muscle	5.9E-02	2.2E-01				
Ovaries	8.7E-02	3.2E-01				
Pancreas	7.9E-02	2.9E-01				
Red Marrow	1.2E-01	4.6E-01				
Bone Surfaces	3.2E-01	1.2E+00				
Skin	4.4E-02	1.6E-01				
Spleen	1.4E-01	5.2E-01				
Testes	5.5E-02	2.0E-01				
Thymus	5.9E-02	2.2E-01				
Thyroid	6.0E-02	2.2E-01				
Urinary Bladder Wall	9.0E-02	3.3E-01				
Uterus	7.9E-02	2.9E-01				
Effective Dose Equivalent	1.1E-01 mSv/MBq	4.1E-01 rem/mCi				

[figure not shown]
Please note that we expect the lung absorbed dose to be much smaller. This is because the mice lungs from which this human absorbed dose was derived had micrometastases in their lungs, secondary to the primary breast cancer. In normal lung mice, the uptake is only 25% of that seen here. Therefore, in the studies with human lungs, free of cancer or cancer metastases, we anticipate much less absorbed radiation dose than presented here.

1.7 Chemistry preparations and controls (CMC)

1.7.1 Preparation

The preparation will consist of 20 μg of the peptide in 4 μL of sterile 0.1M acetate buffer pH = 4.6, to which will be added 400 μL of 0.2 M glycine buffer, pH = 9, 100 μg of SnCl2·2H₂O in 20 μL 0.05M HCl, and 1000 μg of glucoheptonate in 20 μL sterile water, and up to 10 mCi of Cu-64 in 1-2 μL 0.1M HCl. The mixture will be heated for 90 min. at 50°C. (Please note: Since we have increased the dose to be administered, we have increased the quantity of radioactivity to be added to the vial. This has changed the incubation time and temperature. This change has no influence on the pharmacokinetics or the biological activity of the preparation).

HPLC analysis will be performed. A typical HPLC profiles given in Fig. 6 shows 97.4% radiochemical purity.

The mixture will then be diluted with 500 μ L of 0.9% sterile NaCl solution, filtered through 0.22 μ filter. 4±10% mCi of this solution will be drawn into a one mL, sterile syringe for injection.

1.8 Clinical Data to Date:

PET Imaging of Human Breast Cancer Using Cu-64-TP3805:

Human BC also overexpresses VPAC1 receptor (Fig. 3). Fig. 2.a, Fig. 2.b and 2.c show that Cu-64 TP3805can detects not only the primary BC (six out of six malignant lesions in four patients studies so far) but also the sentential lymph nodes. These data provide the evidence that the Cu-64-TP3805 analogue data in mouse model, can be successfully translated to accurately image human tumors and provide a confidence that this PC imaging investigation is worthwhile.

In the USA and abroad, prostate cancer (PC) takes thousands of lives every year. Yet its early and accurate detection continues to be challenging. At the onset of PC, VPAC1, which belongs to the superfamily of G-protein coupled receptors, expresses in high density on PC cells, but not on benign or normal cells. Our extensive preclinical findings, and preliminary data in humans, have shown that ⁶⁴Cu-TP3805 has a high affinity for VPAC1, is stable in vivo, and has the ability to image breast tumors in humans and spontaneously grown PC in TRAMP mice. The goal was to determine the ability of ⁶⁴Cu-TP3805 to image PC in men and to evaluate the findings with pathologic examinations.

Methods: 25 men scheduled for radical prostatectomy and who signed IRB approved consent form were PET imaged preoperatively. Standardized Uptake Values (SUVs) were determined, malignant lesions (SUV > 1.0) were counted, and data compared with histologic findings. In addition, de-paraffinized whole mount pathology slides (n=68) from 6 VPAC1 PET imaged patients, 3 benign prostatic hyperplasia (BPH) patients (n=9), one malignant lymph node (n=3), and one benign lymph node (n=3) were incubated with ⁶⁴Cu-TP3805, washed with PBS, dried and subjected to digital autoradiography (DAR). Slides were then H&E stained, read by a pathologist, and DAR images were compared with foci delineated as PC, benign, cyst, or prostatic intraepithelial neoplasia (PIN).

Results: In 25 patients, 212 lesions had SUVs > 1.0 as compared to 127 lesions identified by histology. While the status of the remaining 85 PET lesions remains to be determined, in 68 histological slides from 6 PET imaged patients, DAR identified 105/107 PC foci (missed 2 due to artifact), 19/19 high grade PIN (HGPIN), 2/2 ejaculatory ducts (ED) and 5/5 urethra verumontanum (UV). Additionally, DAR found 9 PC lesions not previously identified by histology. The positive and the benign lymph nodes were correctly identified by DAR, and for the 3/3 BPH patients without PC, and 5/5 cysts, DAR was negative.

Conclusion: ⁶⁴Cu-TP3805, a VPAC1 receptor specific biomolecule delineates PC lesions in vivo and ex vivo, provides normal images for benign masses, and is worthy of further studies in patients.

In this investigation, we will use the same preparation, Cu-64-TP3805 that has been prepared and used in the previous human subjects with 100% success. Although no preparation will either be compounded or used out of the Jefferson campus, we will use a "kit" that will be ready to be heated following the

addition of 440 μ L of sterile H2O and then Cu-64 activity. These kits will contain all chemicals in sterile, 10 mL glass vials. Reagents will be added to the vial, snap frozen in dry ice, lyophilized and the vials will be sealed in N2 atmosphere. They will be stored at 4°C and examined for Cu-64 labeling and shelf life stability.

Such preparations will be convenient and assure consistency of reagents. Such kits prepared previously in our laboratory were stable for more than two years. We expect similar stability, but will be used only after careful examination of their reproducible and stable preparations, as examined by HPLC. There will be only one patient studied at a time. The syringe containing the Cu-64-TP3805 will be clearly labeled with patient's name. "Cu-64-TP3805" name, the amount of radioactivity, and the time at which the dose was dispensed.

Please note that under this eIND 101550 and with all institutional approvals, the agent was administered to nineteen females with known BC. All malignant lesions including involved lymph nodes were unequivocally delineated (100%). There were no adverse events except three patients sensed flushing which resolved without any medication within a few minutes. Therefore, we will not change this preparation (Cu-64-TP3805). A preprint (J Nucl Med July 2013) of this investigation, reference [79].

1.9 Dose Rationale and Risk/Benefits

During the nineteen BC patient studies as per the suggestion by the FDA, a dose escalation study was performed using 3 mCi±10% (n=2), 3.5 mCi±10% (n=2), and 4 mCi±10% (n=2). From these studies, it was concluded that the image quality was much better with a 4 mCi±10% Cu-64-TP3805 dose while the radiation dose (liver target organ) to the liver and all other organs were well within the dose delivered by routine diagnostic nuclear medicine procedures. Based on this, FDA approved the use of 4 mCi±10% dose to the next thirteen patients. In this PC PET study therefore, we will use 4 mCi±10% dose which is also approved by the FDA (eIND 101550) for this PC PET study. We will strictly adhere to this dose.

2.0 STUDY OBJECTIVES

2.1 Primary Objective:

The primary objective of this study is to assess the ability of Cu-64-TP3805 to detect Prostate cancer in patients with persistently elevated PSA.

3.0 STUDY DESIGN

3.1 General Design

This is a single institution, open-label pilot phase I feasibility diagnostic imaging study.

3.2 Primary Study Endpoints

The primary endpoint of study will be to determine the ability of Cu-64-TP3805 to detect PC foci within the prostate gland in patients with persistialy elevated PSA as compared with tumor maps derived by histology of biopsy specimens obtained guided biopsy.

3.3 Primary Safety Endpoints

As stated previously in section 1.9, we will use 4 mCi±10% Cu-64-TP3805 dose given with FDA approval to fifteen of the nineteen BC patients. The peptide quality (20 µg) will also be kept unchanged.

There was no toxicity in this entire study of the nineteen subjects except three subjects sensed flushing which resolved within minutes without any medication. It is reasonable therefore to anticipate that in this PC study too, there will be no adverse events (AE) due to dose administered. Nevertheless, a physician (either [name] or [name]) will be available during and after the injection. An up to date first aid box will be available. The Research Coordinator will call each subject 24 hrs later and make note of any AE patients may have experienced.

4.0 SUBJECT SELECTION AND WITHDRAWAL

4.1 Inclusion Criteria

Subjects must meet all of the following criteria to be enrolled in this study:

- 1. Male aged 21 years or older.
- 2. Ability to provide signed informed consent and willingness to comply with protocol requirements.
 - 3. Have persistently elevated PSA.
 - 4. Scheduled to have biopsy at least 7days post Cu-64.
- 5. Agree to use an acceptable form of birth control for a period of 7 days after the Cu-64-TP3805 injection.

4.2 Exclusion Criteria

Subjects must not meet any of the following criteria to be enrolled in this study:

- 1. Participating would significantly delay the scheduled standard of care therapy.
- 2. Administered a radioisotope within 10 physical half-lives prior to study drug injection.
- 3. Have any medical condition or other circumstances that, in the opinion of the investigator, would significantly decrease obtaining reliable data, achieving study objectives or completing the study.

4.3 Gender/Minority/Pediatric Inclusion for Research

This study will include men of any race or ethnicity who meet eligibility criteria. As PC is a disease of middle aged and older men, no women or pediatric patients will be included.

4.4 Subject Recruitment and Screening

A total of 20 patients with persistently elevated PSA, presented at Urology Associates Office of TJU, and are scheduled for a biopsy, will be enrolled. Drs. [name], [name], and [name] shall determine the patient eligibility, and inform the PI, [name], and the research coordinator, [name]. Each patient shall sign an IRB approved consent form. Each patient shall be administered IV with 4 mCi ± 10% Cu-64-TP3805.

4.5 Early Withdrawal of Subjects

4.5.1 When and How to Withdraw Subjects

Patients who withdraw consent or who do not complete the investigational imaging or who do not have radical prostatectomy will be withdrawn from study and will not be included in the analysis.

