4.5.2 Data Collection and Follow-up for Withdrawn Subjects

Withdrawn subjects will be removed from the analysis and no follow up will be undertaken.

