7.0 STATISTICAL PLAN

7.1 Sample Size Determination

7.2 We will study 20 patients with persistently elevated PSA for a Cu-64 PET imaging in whom biopsy are ordered. These patients shall be PET imaged with our Cu-64 peptide probe first and then a week or so later the image guided biopsy shall be performed. The image guided biopsy is the standard of care procedure. The objective is to validate the PET imaging results with the histology of biopsy results. Generally, approximately 60% of the patients with elevated PSA have prostate cancer. We expect 80% accuracy in identifying 20 subjects as having histologically determined cancer/absence of cancer. The 95% confidence interval of this level of accuracy for this sample size is + or – 17.5%. Thus we expect to find an accuracy level between 62.5% to 97.5%. Please note this is a pilot study, not designed to be an efficacy determination trial. **Statistical Methods**

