7.3 Subject Population(s) for Analysis

20 subjects completing the investigational imaging and undergoing biopsy and PET imaged with 4 mCi ± 10% Cu-64-TP3805.

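### Section 4.5.1 drops every man without a radical prostatectomy, contradicting section 7.3 and removing the biopsy-negative men that the accuracy estimate needs

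*Combined protocol and SAP*

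**What the plan says.** Section 4.5.1 lists who leaves the study. Besides men who withdraw consent or do not complete the imaging, it names those "who do not have radical prostatectomy will be withdrawn from study and will not be included in the analysis". Section 4.5.2 confirms the consequence: "Withdrawn subjects will be removed from the analysis and no follow up will be undertaken".

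The rest of the protocol rests on biopsy:

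- Section 4.4 enrols "A total of 20 patients with persistently elevated PSA" for whom a biopsy is already planned, and the procedural inclusion criterion in 4.1 is "Scheduled to have biopsy at least 7days post Cu-64".
- The primary endpoint in 3.2 compares PET with histology of the guided-biopsy specimens.
- The sample-size text in 7.1/7.2 reads "We expect 80% accuracy in identifying 20 subjects as having histologically determined cancer/absence of cancer".
- Section 7.3 defines the analysis population as "20 subjects completing the investigational imaging and undergoing biopsy", with no mention of surgery.
- The visit chart in 15.1 ends once the biopsy pathology has been received.

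Prostatectomy appears as the source of histology only in the earlier cohort summarised in section 1.8, which imaged "25 men scheduled for radical prostatectomy".

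**The concern.** Under 4.5.1 a man is analysed only if he has an operation that follows from the reference result. A man whose biopsy is benign would not be expected to have it, and a man whose cancer is managed another way would not have it either. The first group supplies all the patient-level true negatives and false positives. Without it, the accuracy described in 7.1/7.2, which counts correct calls of both cancer and absence of cancer, cannot be estimated. What remains is sensitivity among operated cancers, still labelled accuracy.

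False positives are an open question for this agent. In the earlier cohort (section 1.8), PET showed 212 lesions above the SUV threshold against 127 on histology, and the status of the other 85 was undetermined. The biopsy-negative men are the ones who can show, at patient level, whether the scan lights up without cancer.

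**Working it through.** **Inputs.** N = 20, expected accuracy 80%, cancer rate 60% and 95% half-width 17.5 points (all from 7.1/7.2); exclusion rule (4.5.1, 4.5.2); replacement only of men consented but not dosed (7.4). Two inputs are not in the documents and are assumptions: men with a benign biopsy do not have a prostatectomy, and a fraction r of men with cancer do (range 25% to 100%).

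**1. The plan's own figure.** The half-width is 1.96 × √(p(1 − p)/n). With p = 0.80 and n = 20, 1.96 × √(0.16/20) = 0.175, giving 62.5% to 97.5%. The stated interval is reproduced, and it needs all 20 men in the denominator.

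**2. Who is left under 4.5.1.** Cancer: 20 × 0.60 = 12. No cancer: 20 × 0.40 = 8, all excluded. Retained: 12 × r.

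| Share of cancers operated (assumed) | Men retained | Without cancer | Half-width at 80% |
|---|---|---|---|
| 100% | 12 | 0 | ±22.6 points |
| 75% | 9 | 0 | ±26.1 points |
| 50% | 6 | 0 | ±32.0 points |
| 25% | 3 | 0 | not meaningful |

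These half-widths use the plan's formula only for comparison. At n = 12 the upper limit would be 80 + 22.6 = 102.6%, which is impossible. Exact (Clopper-Pearson) intervals show the same loss: 16/20 gives 56.3% to 94.3%, 10/12 gives 51.6% to 97.9%, and 5/6 gives 35.9% to 99.6%.

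The loss is larger at the benign rate in the protocol's background. Section 1.2 puts benign biopsies above 65%. At 65%, 20 × 0.65 = 13 men would be excluded and at most 7 retained.

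**3. What the retained men measure.** In all 20 men, accuracy = 0.60 × sensitivity + 0.40 × specificity. Under 4.5.1 it reduces to sensitivity.

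| Sensitivity | Specificity | Accuracy, all 20 men | Reported under 4.5.1 |
|---|---|---|---|
| 100% | 50% | 0.60 + 0.20 = 80% | 100% |
| 70% | 95% | 0.42 + 0.38 = 80% | 70% |
| 100% (always positive) | 0% | 12/20 = 60% | 12/12 = 100% |

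Two scans that both meet the plan's 80% expectation would be reported 30 points apart, and a scan with no discrimination would look perfect.

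**4. Losses are not made up.** Section 7.4 replaces only men who were not dosed. Men removed by 4.5.1 have already been imaged, so they are not replaced. Ending with 20 analysable men would take 20/0.60 = 33.3, so 34 enrolled, even if every cancer were operated, and 20/(0.60 × 0.50) = 66.7, so 67, if half were. All 20 would still have cancer.

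**The case against.** The strongest reply is that the harm is conditional. Section 7.3, which defines the analysis set, is biopsy-based, as are eligibility, endpoint, sample size and visit chart. No visit after biopsy is scheduled at which surgery could be recorded. On that reading the clause in 4.5.1 is a stray remnant that nobody would apply. The likely intent is indeed clear, and the loss occurs only if 4.5.1 is followed. But 4.5.1 is an explicit exclusion, 4.5.2 reinforces it, and the protocol gives no order of precedence. Left unresolved, the conflict lets the denominator be chosen after the results are known.

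Other points narrow the claim without overturning it:

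- That biopsy-negative men do not have prostatectomy is an assumption. It is a safe one, since no section plans surgery for anyone.
- Specificity is not a named endpoint. Accuracy for cancer and its absence is, and it needs the same men.
- The argument holds at patient level. The endpoint in 3.2 speaks of foci and the case report form records them by sextant, so operated men could still supply negative regions. No such analysis is specified.
- That the clause was carried over from the earlier prostatectomy cohort is an inference.
- The study is a pilot, not designed to determine efficacy. That excuses imprecision, not exclusion that depends on the outcome.

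**Conclusion.** The concern holds, and the text must be corrected. Sections 4.5.1 and 7.3 give incompatible analysis populations, and 4.5.1 taken literally makes the stated patient-level accuracy unattainable. At the plan's 60% cancer rate it removes 8 of 20 men, leaves at most 12 and reduces the specificity denominator from about 8 to 0. The change of estimand matters more than the lost precision. The size rests on the plan's cancer rate and on benign-biopsy men not being operated; how far the retained number falls below 12 depends on a surgery rate that the documents do not give.

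**What to change.** In 4.5.1, replace the prostatectomy condition with absence of the protocol's image-guided biopsy (the standard-of-care procedure named in 7.1/7.2), so that it agrees with 7.3. Add one sentence stating that every man with completed imaging and available biopsy histology is analysed, whatever the biopsy result or later treatment.

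In the same amendment, state in 7.4 whether men dosed but not biopsied are replaced, because 20 evaluable men are otherwise not assured, and require all exclusions after dosing to be reported with reasons.

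The cost is a short protocol amendment made before analysis, with no extra procedures and no change to clinical care. The 4.5.1 correction itself needs no extra patients. With all 20 men analysed, about 12 with cancer and 8 without are expected and the plan's ±17.5 points applies again. Specificity would still be imprecise: 7/8, for example, has an exact 95% interval of 47.3% to 99.7%.
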